Protocol Summary

Rejuvenation of Aged Muscle Stem Cells Through Exercise

BACKGROUND AND SIGNIFICANCE: Continuous physical exercise is a potent method of preserving muscle mass with aging. In terms of muscle stem cell (referred to as satellite cells) health, exercise rescues the aging-associated loss of satellite cells and improves the ability to regenerate muscle after injury. The mechanisms for exercise-induced improvements in satellite cell function are currently unclear. However, exercise has been shown to induce AMPK activity, autophagy and decrease apoptosis in muscle. Moreover, autophagy regulates satellite cell mitochondrial function and proliferative capacity in young and old satellite cells. We have preliminary data showing an exercise-induced increase in autophagy and proliferation in aged satellite cells in the mouse. Based on these findings it is justifiable to investigate the effect of exercise training on satellite cell autophagy/apoptosis in young and aged human's populations to ensure translational capacity to our research program. We hypothesize that exercise will increase muscle stem cell function in young and older individuals through induction of cellular autophagy and survival mechanisms.

FUNDING SOURCE: [name], Ph.D. will be the Principal Investigator for this study. [name], M.D. and [name], M.D. will be the physicians and Co-Investigators on this study. The study will be funded by the National Institutes of Health/National Institute on Aging.

PURPOSE OF STUDY: The proposed study will establish a newly-identified signaling pathway regulating both autophagy and apoptosis in human satellite cells. These findings will allow for novel pharmacological targets in satellite cells to return regenerative capacity to elderly individuals.

DESIGN AND PROCEDURES: Up to 80 adults, 21 years of age and greater, will undergo a consent visit followed by three blood draws and muscle biopsy visits- baseline (pre), after the first exercise bout (post-acute), and after the 12 week training program (post-chronic). Blood will be obtained and tested for inflammatory (IL-6/TNF/IL-1) and endocrine markers (Testosterone/Estrogen/Thyroid hormone). As part of the intervention, participants will undergo moderate intensity treadmill exercise three times per week for 10-12 weeks or serve as sedentary controls. The specifics of the biopsy visits are described in the consent and have been repeated here:

- **Visit 1:** The consent visit will take place at the Duke Center for Living and will last one hour. We will explain the study and the consent form in detail and on an individual basis.
- **Visit 2:** This 1-hour visit will take place at the Center for Living.
 - A brief medical history including list of medications will be performed.
 - A blood sample of up to 20 mL will be collected from consented participants through venipuncture.
 - A baseline muscle biopsy procedure will be performed by either [name] M.D. or [name] M.D., both of whom have extensive experience with this procedure in previous studies. The subject will be told to avoid products such as aspirin medication up to five days before this visit to reduce the risk of excess bleeding from the biopsy incision site (also avoid ibuprofen, naproxen the day before this visit). After local anesthesia (xylocaine, 2%) is injected, a small incision will be made in the left thigh. Four to six small pieces of muscle about the size of a pea will be surgically removed. The incision site will be closed using steri-strips. This part of the visit takes approximately 30 minutes. All muscle samples will be stored in a -80°F freezer at the Duke Molecular Physiology Institute.

The Exercise Training Program: After Visit 2, subjects will be randomized to one of two intervention groups. Group 1 will be required to attend 3 supervised exercise sessions per week for 10-12 weeks. They will be fitted with a heart rate monitor around the chest to maintain running intensity. Each exercise session will begin with a short warm-up before performing submaximal (70% age predicted heart rate) exercise on a treadmill or stationary bicycle for 30 minutes. Group 2 will be the sedentary control group. This group will be asked to maintain their baseline level of inactivity.

- **Visit 3:** This 1-hour visit will take place at the Center for Living. For those participants assigned to exercise intervention, this will take place approximately 2-hours after the first bout of exercise. For the control participants, this visit will occur approximately 1 week after the baseline visit.
 - This visit will follow the same procedures as Visit 2, described above.
- **Visit 4:** This 1-hour visit will take place at the Center for Living. For those participants assigned to exercise intervention, this will take place approximately 2-hours after the final bout of exercise. For the control participants, this visit will take place approximately 10-12 weeks after Visit 3.
 - This visit will follow the same procedures as Visit 3, described above.

STUDY DURATION: The study timeline for this protocol is 14-18 weeks depending on participant and study staff availability. In addition to the study visits listed above, the participants may be asked to come to the Center for Living to exercise on a treadmill or stationary bicycle three times a week for 10-12 weeks.

SELECTION OF SUBJECTS: Study participants will include adults 21 years and older who are not currently participating in regular physical exercise or weight reduction dieting. Inclusion/exclusion criteria are listed below.

The following **INCLUSION** criteria must be met:

- Age 21 years or greater.
- No medication changes within the last 3 months.
- Not participating in regular physical exercise (more than 60 minutes of moderate intensity or 30 minutes of vigorous intensity exercise per week).
- Able to decide if you want to take part in the study.

The following criteria will **EXCLUDE** potential participants from participating in the study:

- Smoker: Tobacco use within the last 12 months.
- Dieting or intending to diet.
- Use of potential confounding medications, e.g. using ticlopidine, clopidogrel, dipyridamole, warfarin, heparin, enoxaparin and other blood thinners.
- Coronary stents or any other medical condition for which aspirin cannot be temporarily withheld.
- Use of hormone replacement medications.
- Absolute contra-indications to exercise: Recent (<6 months) acute cardiac event unstable angina, uncontrolled dysrhythmias causing symptoms or hemodynamic compromise, symptomatic aortic stenosis, uncontrolled symptomatic heart failure, acute pulmonary embolus, acute myocarditis or pericarditis, suspected or known dissecting aneurysm and acute systemic infection.
- Relative contra-indications to exercise: Left main coronary stenosis, moderate stenotic valvular heart disease, outflow tract obstruction, high degree AV block, ventricular aneurysm, uncontrolled metabolic disease (e.g. diabetes, thyrotoxicosis, myxedema), uncontrolled pulmonary disease (e.g. severe COPD or pulmonary fibrosis), mental or physical impairment leading to inability to exercise adequately.
- Have a confounding medical condition that is progressive and unstable such as HIV, Hepatitis C, active cancer, and/or taking medications for those conditions.

- Unwillingness to be randomized to any one of two intervention groups, submit to skeletal muscle biopsies and all other study testing or continuously participate in a randomly assigned exercise training or program for three months.
- Orthopedic limitations, musculoskeletal disease and/or injury.
- Allergic to xylocaine.
- Unwillingness to exercise at the Duke Center for Living during staff supervised times.

SUBJECT IDENTIFICATION, RECRUITMENT AND COMPENSATION: Study recruitment will occur primarily through local newspaper advertisements in the Herald Sun, Inside Duke, Duke Healthline, the Duke Clinical Research website, and word-of-mouth. Interested participants will be directed to contact the study office via phone. Following an initial phone or personal screening questionnaire, eligible and interested participants will be scheduled for a consent visit and a member of the PI's study staff will obtain informed consent prior to scheduling testing visits. Participants will receive \$400 total compensation for completion of the study. Participants will receive \$100 for completion of Visit 2, and \$150 each for Visits 3 and 4.

SUBJECT COMPETENCY: Subjects must be able to speak and understand English to participate in this study.

RISK/BENEFIT ASSESSMENT: Participation in this study may lead to increased risk for the following side effects. Participants may discuss these with the study doctor and your regular health care provider if they choose. There may be risks, discomforts, or side effects that are not yet known. The known risks are:

- Thigh Muscle biopsies may result in momentary pain and discomfort, burning or bleeding, numbness, and rarely fainting or infection. Please notify [name] or study staff if you have taken any product containing aspirin within five days of the muscle biopsy as aspirin can increase bleeding risk. The incision site may leave a scar and muscle soreness may be present up to ten days after the biopsy.
- Xylocaine: While the local numbing medicine xylocaine is almost entirely free from allergic properties (such as causing hives), an allergic reaction is possible, and the participant will not be given xylocaine if they have a history of such a reaction. The xylocaine will be given by a small injection into the skin at the site of the muscle biopsy.
- Risks associated with a standard blood draw include momentary discomfort and/or bruising. In addition, there is a minimal risk of infection, excess bleeding, clotting, and fainting.
- An exercise program may result in muscle, bone and/or joint soreness, discomfort and/or injury.

Any adverse events will be reviewed and signed off on by the PI as they occur. Adverse events will then be reported to the IRB in accordance with HRPP policies.

Participants may benefit from the exercise portions of this study through improved physical function and cardiorespiratory fitness

COST TO THE SUBJECT: The subjects will not incur any costs as a result of participation in this study. Immediate necessary care is available if an individual is injured because of participation in a research project. However, there is no provision for free medical care or for monetary compensation for such injury. During this study, hospitalizations or additional care beyond the scope of this study will be the responsibility of patients and/or their insurance company.

DATA ANALYSIS AND STATISTICAL CONSIDERATIONS: Muscle stem cell function will be compared across age groups at each time point using a One Way ANOVA or t test for specific comparisons. An alternative analysis will be a longitudinal design following muscle stem cell function from each individual before and after exercise training. This analysis will be performed with repeated measure ANOVAs. Data will

be analyzed using GraphPad Prism 6 statistical software. Significance will be accepted as $p < .05$.

DATA STORAGE AND CONFIDENTIALITY: All collected data will be stored in a locked file to be accessed only by [name] and his study staff. Study records that identify subjects will be kept confidential as required by law. Federal Privacy Regulations provide safeguards for privacy, security, and authorized access. Except when required by law, they will not be identified by name, social security number, address, telephone number, or any other direct personal identifier in study records disclosed outside of Duke University Health System (DUHS). For records disclosed outside of DUHS, they will be assigned a unique code number. The key to the code will be kept in a locked file in [name] office.

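### The single heart-rate target overshoots the intended moderate dose for a participant whose exercise heart rate is materially lowered by a stable drug, and no alternative target is given

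*Protocol*

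**What the plan says.** **Intensity.** The Exercise Training Program section of the protocol has Group 1 "performing submaximal (70% age predicted heart rate) exercise on a treadmill or stationary bicycle for 30 minutes". The control is a chest monitor: "They will be fitted with a heart rate monitor around the chest to maintain running intensity". No perceived-exertion, workload or measured-peak criterion is given. Design and Procedures states the intent in words only: "participants will undergo moderate intensity treadmill exercise three times per week".

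**Who may enrol.** Under Selection of Subjects, adults from 21 upward qualify, with no upper age limit. The medication condition is stability: "No medication changes within the last 3 months". The drug exclusion is open-ended, but every example affects clotting: "Use of potential confounding medications, e.g. using ticlopidine, clopidogrel, dipyridamole, warfarin, heparin, enoxaparin and other blood thinners". The absolute cardiac exclusions cover recent, unstable or uncontrolled disease, such as "uncontrolled dysrhythmias causing symptoms or hemodynamic compromise, symptomatic aortic stenosis, uncontrolled symptomatic heart failure". The relative ones add structural disease, high-grade heart block and uncontrolled metabolic or pulmonary disease. Coronary stents, and conditions in which aspirin cannot be paused, are also excluded. Treated, controlled high blood pressure is not on any list.

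**Information on drugs.** At Visit 2, "A brief medical history including list of medications will be performed". Nothing links that list to the exercise prescription.

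**First biopsy after exercise.** For the exercise group's Visit 3, "this will take place approximately 2-hours after the first bout of exercise".

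**The concern.** A target computed from age assumes that the participant's maximum heart rate is close to the predicted one. A drug that lowers exercise heart rate breaks that link. The person has to work relatively harder to reach the written number, and the monitor is there to hold them to it. The result can depart from the moderate, submaximal dose that the protocol intends.

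At stake are the dose and the safety of a previously inactive participant on such a drug. The first session deserves particular care. It is one of 30 to 36 sessions (3 × 10 to 3 × 12), but it alone is the exercise that precedes the Visit 3 biopsy, so a correction in week 2 comes too late for that exposure. Supervising staff may well adjust, but the text gives them no value to adjust to, and two staff members could choose differently.

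**Working it through.** The protocol contains no calculation to reproduce. The check is direct arithmetic on the written target.

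**Input from the protocol**
- Target: 70% of an age-predicted heart rate. The prediction equation is not stated.

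**Assumptions, not in the protocol**
- The 70% refers to the age-predicted maximum, P.
- Without the drug, the participant's own maximum equals P.
- The drug lowers it by a fraction r, with r from 5% to 20%, so own maximum is P(1 − r).
- For beats per minute only, P = 220 − age.
- The upper limit of moderate is taken in turn as 75%, 80% and 85% of own maximum.

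**Step 1. Share of own maximum at the written target.** The share is 0.70 × P / [P(1 − r)] = 0.70/(1 − r). P cancels, so the result depends on neither age nor the prediction equation.

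| Fall r | 0.70/(1 − r) | Limits exceeded |
|---|---|---|
| 0% | 70.0% | none |
| 5% | 0.70/0.95 = 73.7% | none |
| 10% | 0.70/0.90 = 77.8% | 75% |
| 15% | 0.70/0.85 = 82.4% | 75%, 80% |
| 20% | 0.70/0.80 = 87.5% | 75%, 80%, 85% |

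**Step 2. Fall needed to pass a limit b.** Solving 0.70/(1 − r) = b gives r = 1 − 0.70/b. For b = 75%, 80% and 85%, r = 6.7%, 12.5% and 17.6%.

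**Step 3. The gap in beats.** The written target exceeds 70% of own maximum by 0.70 × r × P.
- Age 30: P = 190 and the target is 133 bpm. At r = 10%, own maximum is 171, 70% of it is 119.7, and the gap is 13.3 bpm. At r = 20%, own maximum is 152, 70% of it is 106.4, and the gap is 26.6 bpm.
- Age 70: P = 150 and the target is 105 bpm. At r = 10%, own maximum is 135, 70% of it is 94.5, and the gap is 10.5 bpm. At r = 20%, own maximum is 120, 70% of it is 84, and the gap is 21 bpm.

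**Step 4. A different reading of the 70%.** Suppose it meant heart-rate reserve, with resting rate H used in both targets. The written target is H + 0.70(P − H), and the one based on own maximum is H + 0.70[P(1 − r) − H]. The difference is again 0.70 × r × P, so the direction is the same.

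**The case against.** The strongest case against has four parts.

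- **The size is assumed.** The protocol supplies only the 70%. The drug effect, the meaning of the target and the limit of moderate all come from outside it. Any age-based target is also imprecise for everyone, and a weak drug effect has not been shown to stand out from that. This stands. It limits the point to a material fall in exercise heart rate. A reader might infer that every user of such a drug is dosed too high. The table does not support that, because a 5% fall passes none of the assumed limits.
- **Safeguards exist.** Sessions are supervised, physicians are co-investigators, and drugs are listed before randomization. Contraindications to exercise are excluded, and the open-ended drug exclusion could be stretched to cover these users. The prescription itself also says submaximal, so staff who pushed someone close to their limit would breach it. All this makes rigid application less likely. It still gives no second target, and nothing in the drug exclusion points to these drugs.
- **No consequence is shown.** A reader might infer that the Visit 3 result is distorted, or that dose will differ between age groups because older people take more of these drugs. The protocol gives no count of users, no distribution by age, and nothing to show that one harder bout changes the satellite-cell response. Neither inference is supported.
- **The remedy is a preference.** A perceived-exertion band has not been shown to match 70% of own maximum, and inactive participants may not know the scale at the bout that matters for Visit 3. This is fair. The sponsor should choose the band and explain the scale beforehand. Excluding these users would avoid mixed dosing, but it changes eligibility.

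**Conclusion.** The point holds in a limited form, at low severity. The written rule, followed literally, gives a higher relative intensity than intended to an enrolled participant whose exercise heart rate is materially lowered by a stable drug, and the listed criteria let such a person in. For an assumed fall of 10% to 20% in own maximum, the excess over the intended 70% is about 8 to 18 percentage points. Whether a given case leaves the moderate range depends on a limit that the protocol does not define.

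The conclusion about direction needs only that the drug lowers the participant's maximum below the predicted one. The size rests on the assumptions listed above. The point concerns individual dose and safety. It is no finding of bias in any comparison, and it would have no practical effect if no such person enrolled.

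**What to change.** Add to the Exercise Training Program: *Participants whose Visit 2 medication list includes a beta-blocker or another drug that lowers exercise heart rate (for example diltiazem, verapamil or ivabradine) train from the first session to a pre-specified moderate perceived-exertion band instead of to 70% of age-predicted heart rate. The scale is explained before the first bout. Heart rate and drug use are recorded at each session.*

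A band of 12 to 13 on the 6-to-20 scale is one proposal. The sponsor should fix scale and band in the same amendment, before they are used.

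The cost is a few sentences, a printed scale at the treadmill and bicycle, and a short explanation to the participant. Eligibility, visits and analysis stay as they are, and the medication list, supervision and monitor are already in place. The drawback is that these few participants are dosed on a subjective scale. If use of such drugs happens to vary with age, the dosing method will vary with age too, and the session records keep that visible.

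### Does timing Visit 3 differently in the two arms spoil the post-acute comparison?

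*Protocol*

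**What the plan says.** Under DESIGN AND PROCEDURES, Visit 3 has one timing rule per arm. For exercisers, "this will take place approximately 2-hours after the first bout of exercise". For controls the rule reads: "For the control participants, this visit will occur approximately 1 week after the baseline visit".

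The only statement that places the first bout relative to the baseline biopsy is in The Exercise Training Program: "After Visit 2, subjects will be randomized to one of two intervention groups". That gives an order and no number of days.

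The baseline visit (Visit 2) includes a biopsy that removes four to six pieces of muscle, for which "a small incision will be made in the left thigh". For Visit 3 the protocol says: "This visit will follow the same procedures as Visit 2, described above".

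Visit 4 comes about 2 hours after the last bout of a 10-12 week programme in exercisers. For controls: "For the control participants, this visit will take place approximately 10-12 weeks after Visit 3".

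STUDY DURATION gives an overall timeline of 14-18 weeks that varies with availability. DATA ANALYSIS AND STATISTICAL CONSIDERATIONS names a comparison of age groups at each time point and, as an alternative, a within-person repeated-measures analysis.

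**The concern.** Controls have no first bout, so their Visit 3 biopsy serves mainly as a reference for the exercisers' post-acute biopsy. A good reference should differ from the exercise sample only by the bout. Here time since the baseline biopsy is set at about 1 week in controls and left open in exercisers.

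The outcome makes this look more serious than an ordinary gap in visit windows. A biopsy is a small muscle injury. BACKGROUND AND SIGNIFICANCE says that exercise, in terms of satellite cell health, "improves the ability to regenerate muscle after injury", so the cells under study are linked to repair. Read literally, Visit 3 samples the left thigh again. If recovery from the first biopsy were still under way in one arm and over in the other, the difference could add to the effect of a single bout or hide it. Variable intervals among exercisers could also add noise to their own change from Visit 2 to Visit 3.

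**Working it through.** The protocol states no figure for the exercisers' interval, so there is nothing to reproduce. The check sets the timing rules side by side and asks how far the overall timeline constrains them.

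**Inputs**
- Controls, Visit 2 to Visit 3: about 1 week (Visit 3).
- Exercisers, Visit 2 to first bout: not stated; call it x. Visit 3 then falls at x plus about 2 hours.
- Training: 10-12 weeks (The Exercise Training Program).
- Controls, Visit 3 to Visit 4: 10-12 weeks (Visit 4).
- Overall timeline: 14-18 weeks (STUDY DURATION). Its start and end are not defined; I assume consent to Visit 4.

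**What the timeline leaves for x**

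Time outside training = timeline − training length. The text does not link particular ends of the two ranges, so all four pairings count:
- 14 − 12 = 2 weeks
- 14 − 10 = 4 weeks
- 18 − 12 = 6 weeks
- 18 − 10 = 8 weeks

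This time covers consent to Visit 2 plus x. So x lies between just above 0 and just under 8 weeks, the top being reached only if almost no time passes before Visit 2. Relative to the controls' 1 week, the range is from 0 − 1 = −1 week to 8 − 1 = +7 weeks.

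**Can the timeline show that the arms are equal?**

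No. For a timeline T and training length L, exercisers have T − L weeks outside training, and controls have T − (1 + L) weeks outside their two biopsy intervals. The difference, (T − L) − (T − 1 − L) = 1 week, holds for every T and L, because the controls' 1 week was put in. It says nothing about x. The timeline neither supports nor excludes equality.

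**Visit 4**
- Controls, Visit 3 to Visit 4: 10-12 weeks.
- Exercisers, first bout + 2 hours to last bout + 2 hours: about the length of training, 10-12 weeks.
- Controls, baseline biopsy to Visit 4: 1 + 10 = 11 to 1 + 12 = 13 weeks.

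Time since the most recent biopsy is therefore matched at Visit 4, and the baseline biopsy is at least about 10 weeks past in both arms.

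**Named analyses**

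The first compares age groups at each time point; nothing suggests that x depends on age. The second follows each person over time. Neither is an exercise-versus-control test at Visit 3.

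**The case for a change.** The strongest case for a change is that visit timing belongs in the protocol and that no analysis can restore equal intervals afterwards. Participants are randomized to a control group that is biopsied at Visit 3, so an arm contrast there is plainly foreseeable even though it is not named. RISK/BENEFIT ASSESSMENT allows for soreness for up to ten days after a biopsy. The controls' interval of about 7 days falls inside that period, while the exercisers' could fall inside or well outside it. A common window would add no visits and no biopsies.

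Part of this stands. The protocol does not guarantee equal time since biopsy, an arm contrast at Visit 3 is plausible, and variable intervals could add noise to within-person change.

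The rest does not carry the point. The ten-day figure concerns soreness and says nothing about satellite cells. The background sentence describes what exercise does; it does not say that a small earlier biopsy changes autophagy, apoptosis or cell function in a later sample. The site within the thigh is not stated, so whether Visit 3 draws on affected tissue is unknown. A same-site rule would add nothing, since Visit 3 repeats the Visit 2 procedures with no distinction by arm. Days between biopsies follow from the visit dates, assuming these are recorded in the usual way, and an analyst can report or adjust for them without a change to the plan.

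**Conclusion.** No change is called for. The observation is correct as a statement of what the protocol leaves open: controls have a stated interval of about 1 week and exercisers have none. But the two rules must be worded differently, because controls have no bout, and about 1 week is a natural counterpart to a first session held at about that time. It is a gap in detail that study staff can fill sensibly when they book that session.

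No size or direction of bias can be given. The range of about 1 week shorter to about 7 weeks longer in exercisers rests on three assumptions: the timeline runs from consent to Visit 4, the ends of the ranges pair freely, and almost no time passes before Visit 2 at the upper extreme. It marks what the text does not exclude and is not evidence of imbalance. The possible effect is confined to one of three biopsy visits and to a contrast that the analysis section does not name. Visit 4, which addresses the training effect, is matched on time since the last biopsy. Following the plan as written is not shown to give a wrong or worse result.

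### The unadjusted age-group comparison of stem cell function is open to confounding by sex mix and by hormonal contraceptive use

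*Protocol*

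**What the plan says.** **Eligibility (Protocol, SELECTION OF SUBJECTS).** The one hormone criterion excludes "Use of hormone replacement medications". It does not define replacement and has no age or sex limit. A second drug criterion excludes "Use of potential confounding medications, e.g. using ticlopidine, clopidogrel, dipyridamole, warfarin, heparin, enoxaparin and other blood thinners"; it is open-ended, but every example is a blood thinner. Stable users of other drugs may enter under "No medication changes within the last 3 months". The age rule is "Age 21 years or greater", with no upper limit, no age bands, and no sex quota or matching. Pregnancy and hormonal contraception appear nowhere in the criteria.

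**Measurements (Protocol, DESIGN AND PROCEDURES).** Blood is tested for testosterone, estrogen and thyroid hormone, and a medication list is taken at Visit 2. The protocol does not say that either enters an analysis.

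**Analysis (Protocol, DATA ANALYSIS AND STATISTICAL CONSIDERATIONS).** The first-named analysis has stem cell function "compared across age groups at each time point using a One Way ANOVA or t test". The alternative is longitudinal, "following muscle stem cell function from each individual before and after exercise training", by repeated-measures ANOVA. Randomisation is between exercise and sedentary control only.

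**The concern.** Nobody is randomised to an age group. The young-versus-old difference is an observational contrast, and the stated tests have age group as their only factor. Any other characteristic that affects stem cell function and is distributed differently between the age groups will appear as part of the age difference.

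Two such characteristics are left open.

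- **Sex.** Nothing in the criteria or the design keeps the share of women similar across age groups.
- **Exogenous hormones.** By excluding replacement and measuring sex-related hormones, the protocol treats hormone status as relevant. It still leaves in hormonal contraception, which would be expected mostly in younger women. One source of exogenous hormones is removed, while another that is probably linked to age stays in.

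What is at stake is how the cross-sectional age difference is interpreted. Part of it could reflect who was recruited.

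**Working it through.** The protocol gives no effect size, SD, power or sex distribution, so there is no figure of its own to reproduce. What follows is a sensitivity check on assumed inputs.

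**Inputs from the protocol.** A cap of 80 participants; two randomised groups; significance at 0.05.

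**Assumptions.** Two age groups of equal size; a two-sided test; n = 40 per age group if all 80 are compared, or n = 20 if the comparison is made within one randomised arm of 40; an effect of sex on stem cell function of 0.3 to 0.8 SD; a difference in female share between age groups of 0 to 50 points.

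**Formulas**
- Bias (SD) = effect of sex (SD) × difference in female share.
- SE = √(2/n), which is √(2/40) = 0.224 or √(2/20) = 0.316.
- Rejection rate with no true age effect = Φ(bias/SE − 1.96) + Φ(−bias/SE − 1.96).

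**Worked case.** With n = 40, a 0.5 SD effect and a 20-point difference, the bias is 0.5 × 0.20 = 0.10 SD and bias/SE = 0.10/0.224 = 0.447. The rejection rate is Φ(−1.513) + Φ(−2.407) = 0.065 + 0.008 = 0.073.

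| Sex effect (SD) | Difference in female share | Bias (SD) | Type I error, n = 40 | Type I error, n = 20 |
|---|---|---|---|---|
| any | 0 points | 0 | 0.050 | 0.050 |
| 0.3 | 20 points | 0.06 | 0.058 | 0.054 |
| 0.5 | 20 points | 0.10 | 0.073 | 0.062 |
| 0.5 | 30 points | 0.15 | 0.103 | 0.076 |
| 0.8 | 30 points | 0.24 | 0.189 | 0.118 |
| 0.8 | 50 points | 0.40 | 0.432 | 0.244 |

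For scale, the difference detectable with 80% power at 40 per age group is (1.96 + 0.84) × 0.224 = 0.63 SD.

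**Contraceptive use, same formula.** Suppose half the young group are women, 30% of them use hormonal contraception, and nobody in the older group does. The difference in user share is 0.5 × 0.30 = 0.15. If use shifted stem cell function by 0.5 SD, the bias would be 0.5 × 0.15 = 0.075 SD. At n = 40 the type I error would be Φ(0.335 − 1.96) + Φ(−0.335 − 1.96) = 0.052 + 0.011 = 0.063.

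**Balanced case.** With equal female shares the bias is zero. With half women in each group and a 0.5 SD effect, sex accounts for 0.5 × 0.5 × 0.5² = 0.0625 of a total variance of 1. Fitting sex would shrink the SE by a factor of about √(1 − 0.0625) = 0.97, a small gain in precision.

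**The case against.** The strongest reply is that the protocol shows no imbalance. Sex confounds an age contrast only if the sex mix differs between age groups, and no mix is given. This stands: every bias figure above rests on an assumed imbalance, and the result is zero without one.

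Five stronger readings are tempting, and the documents do not support them.

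- **The comparison is confounded by sex and hormones.** A missing sex term does not establish this. Natural hormone decline is also part of ageing and lies on the path from age to outcome. Only exogenous use, or pregnancy, is a candidate confounder.
- **The replacement exclusion affects only older people and shifts their sex mix.** The criterion has no age, sex or hormone limit, and could cover thyroid or testosterone replacement at any age.
- **Contraceptive users all fall in the young group.** This is likely, but the protocol gives no age cut-points.
- **A contraceptive effect on a blood marker adds to a sex bias.** A 1 SD shift in a marker among 30% of women, who form half the young group, gives 0.5 × 0.30 × 1 = 0.15 SD on that marker. That is a different outcome from stem cell function, and the protocol states no age comparison of markers. Even on one outcome, the two biases could offset each other.
- **The whole trial is affected.** Exercise versus control is randomised and so balanced in expectation. Within-person change is not biased by a stable sex difference in level, although sex could still modify how change differs by age, and pregnancy would not be stable over 10-12 weeks.

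It can also be said that covariates are often left to a statistical analysis plan, which may exist. But this protocol does not leave the matter open: it names single-factor tests for a non-randomised contrast. Eligibility, for its part, belongs in the protocol.

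**Conclusion.** The point holds in a limited form. The cross-sectional age comparison is open to confounding by sex mix and exogenous hormone use, and nothing in the criteria or the stated analysis prevents it. Whether confounding will occur, and in which direction, cannot be told from the document.

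Under moderate assumptions the effect is small: 0.10 SD of bias and a type I error of about 0.07 at 40 per age group. It becomes material only with a large imbalance and a strong sex effect together. With a balanced sex mix, only a little precision is lost. This is an inexpensive improvement to a secondary weakness; it does not undermine the exercise question.

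**What to change.** 1. In DATA ANALYSIS AND STATISTICAL CONSIDERATIONS, replace the one-way ANOVA or t test across age groups with a model containing age group and sex.
2. Identify hormonal contraceptive users from the Visit 2 medication list, and repeat the age comparison without them as a sensitivity analysis.
3. In SELECTION OF SUBJECTS, state how pregnancy and hormonal contraception are handled, since hormone replacement is excluded and hormones are measured. What that handling should be, including whether either is an exclusion, is for the investigators to decide.

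The cost is one degree of freedom, one sensitivity analysis on somewhat fewer participants, and a few lines of text. No new visit or assay is needed. Adjusting for sex does not remove confounding by other characteristics that differ between age groups, so the age contrast should still be reported as observational.
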